### **4.2 Secondary Objectives**

Secondary and exploratory objectives will be assessed in all study subjects and in the ultra-low risk patient subset

- 4.2.1 To determine the overall response rate at day 28 of treatment
- 4.2.2 To calculate the duration of response
- 4.2.3 To calculate the incidence of serious infections (overall, viral, bacterial, fungal, parasitic) by day 90 of treatment
- 4.2.4 To determine the cumulative steroid exposure through days 28 and 90 of treatment
- 4.2.5 To determine the incidence of 1 year NRM, relapse, overall survival, and chronic GVHD
- 4.2.6 To determine the incidence of steroid-refractory GVHD in patients by day 90 of treatment

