### 10.2.2 Serious Adverse Event

An adverse event is considered “serious” if it results in any of the following outcomes:

- Death
- A life-threatening adverse event  
An adverse event is considered ‘life-threatening’ if, in the view of either the investigator, its occurrence places the patient or subject at immediate risk of death. It does not include an adverse event that, had it occurred in a more severe form, might have caused death.
- Inpatient hospitalization or prolongation of existing hospitalization for  $\geq 24$  hours.
- A persistent or significant incapacity or substantial disruption of the ability to conduct normal life functions
- A congenital anomaly/birth defect
- Important medical event  
Any event that may not result in death, be life-threatening, or require hospitalization may be considered serious when, based upon appropriate medical judgment, they may jeopardize the patient and may require medical or surgical intervention to prevent one of the outcomes listed in this definition of “Serious Adverse Event”. Examples of such medical events include allergic bronchospasm requiring intensive treatment in an emergency room or at home; convulsions that do not result in inpatient hospitalization or the development of drug dependency or drug abuse.

As additional guidance, preplanned hospitalizations or procedures for preexisting conditions that are already recorded in the patient’s medical history at the time of study enrollment should not be considered SAEs.

**The development of steroid-refractory GVHD at any time from study entry to study day 100 will be considered an SAE for the purposes of this study.**

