### 10.2.3 Expected Adverse Events

In this protocol, an adverse event (AE) is considered “expected” if it is described in the Package Insert, in published medical literature, in the protocol, or in the informed consent document.

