#### SAE Reporting

	DCC Reports SAE to:		
	DSMB	Single IRB (NMDP)	Consortium
Note: Sites report these SAEs to DCC from patient consent to study day 56			
All SAEs; ✓ Expected or Unexpected ✓ Not Related, Unlikely, Possible, Probable, or Definite	With scheduled submissions	In summary fashion at the time of IRB continuing review	Monthly
Note: Sites report these SAEs to DCC for events occurring after 56 days			
SAEs – ✓ Unexpected ✓ Probable or Definite	5 days from knowledge  AND	Within 10 working days after the investigator becomes aware of the event	Monthly

	With scheduled submissions		
Note: Sites report these SAEs to DCC for events occurring at any time on study			
SAEs – ✓ All deaths not meeting criteria in above two categories	With scheduled submissions	Within 10 working days if the death meets the criteria for an unanticipated problem as defined in Section 10.5	Monthly

10.4.1 The Principal Investigator must be notified within 3 business day of study team's knowledge of any event meeting the criteria and definition per this protocol in section 10.1 of a serious adverse event, occurring during the study.

10.4.2 The investigator must report all events meeting the criteria and definition of a serious adverse event that are unexpected and possibly related (definite, probable or possible to study treatment administration) to the local IRB as per local IRB policy.

10.4.3 All reportable Serious Adverse Events will be reported using the Serious Adverse Event form within 3 days of first awareness of the event to the MAGIC Data Coordinating Center. A copy of the form should be sent to the MAGIC Coordinator via email to [[contact]](mailto:[contact]).

The MAGIC Data Coordinating Center will disseminate information regarding serious adverse events to the participating sites within 3 days of review of the information by the PI or designee if the event(s) is believed to be related (i.e. probably or definitely) to the study treatment. All other Serious Adverse Events will be discussed on monthly webinars held with all participating centers.

The Principal Investigator will be responsible for reporting of events to the FDA and supporters, as appropriate and defined in the regulations under 21 CFR 312.32.

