### Steroid-refractory GVHD:

We expect a rapid steroid taper to be safe for ultra-low risk patients given the high response rates and very low NRM observed in our preliminary data from patients treated with standard steroid doses. The primary risk to patients is the possibility that a rapid taper of steroids will result in GVHD that is non-responsive even to higher doses of steroids. In order to protect study subjects we have designed a stopping rule that will terminate the trial early if a rapid taper leads to an unacceptable incidence of steroid-refractory GVHD. Our preliminary data show that the incidence of steroid-refractory GVHD by day 100 of treatment using the definition in section 9.1.3 in pediatric patients with low risk (Minnesota standard risk/Ann Arbor 1) GVHD is 15%.

We will monitor the number of cases of steroid-refractory GVHD by day 100 in the entire study population and accrual will be halted if there is sufficient evidence that the rate of steroid refractory GVHD exceeds the acceptable target rate of 15% by more than 20% (35% unacceptable rate). If the cumulative number of patients that experience treatment failure is greater than the associated boundary value  $b_k$  listed in the table below, among the  $k$  patients enrolled in the trial, then accrual will be halted for safety considerations. Specifically, if more than 4 of the first 11 patients or more than 5 of the first 15, etc. develop steroid refractory GVHD, the trial will be halted for safety considerations.

Maximum # of Patients, $k$	Up to 11	12-15	16-19	20-23	24-27	28-32	33-36	37-41	42-46	47-50
Boundary, $b_k$	4	5	6	7	8	9	10	11	12	13

The operating characteristics of this stopping rule are as follows:

	True Steroid Refractory Rate		
	15%	30%	35%
Probability of Early Stopping	0.05	0.75	0.92

Using these boundaries, if the true steroid refractory rate is 15%, 30%, or 35%, the probability of stopping the trial early is 0.05, 0.76, and 0.92 respectively.

All the stopping rules were computed using the `toxbdry` function in R and calculations of this function are based on methods described in Chapter 12 of Jennison and Turnbull and in the illustrative paper by Ivanova, Qaquish and Schell. The boundary crossing probabilities under

the acceptable and unacceptable toxicity rates are 0.05 and 0.90 respectively and the boundaries are calculated starting from 10th patient.

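### The stopping rule counts steroid-refractory GVHD to day 100, but reporting rules for late cases conflict, the denominator is worded two ways, and the stated stopping probabilities ignore follow-up lag

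*Combined protocol and SAP*

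**What the plan says.** **What is counted.** Section 10.6: "We will monitor the number of cases of steroid-refractory GVHD by day 100 in the entire study population". Section 10.2.2 agrees on the window: "The development of steroid-refractory GVHD at any time from study entry to study day 100 will be considered an SAE". Section 14.1 also uses day 100. Section 4.2.6 does not: "To determine the incidence of steroid-refractory GVHD in patients by day 90 of treatment".

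**What must be reported after day 56.** The SAE table in section 10.4 has a row headed "Note: Sites report these SAEs to DCC for events occurring after 56 days". It covers SAEs that are unexpected and also probably or definitely related. A further row covers deaths at any time. Under section 10.2.3 an event is expected "if it is described in the Package Insert, in published medical literature, in the protocol" or in the consent document. Section 10.1 asks for any SAE after day 56 considered related to study treatment, expected or not. Section 10.2.1 limits adverse event reports after day 56 to unexpected or fatal events, and then has an unfinished sentence about serious adverse events.

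**What is scheduled.** In Table 2, GVHD staging and concomitant medication review fall on days 42, 56 and 90. After that there is only the flare column, which footnote 8 limits to the first flare. No visit falls at day 100.

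**The denominator.** One sentence of 10.6 compares failures with the boundary for the k "patients enrolled in the trial, then accrual will be halted for safety considerations". The next sentence halts "if more than 4 of the first 11 patients or more than 5 of the first 15, etc. develop steroid refractory GVHD". Accrual is continuous. The stated stopping probabilities are 0.05, 0.76 and 0.92 at true rates of 15%, 30% and 35%; the small table prints 0.75 at 30%.

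**The concern.** Section 10.6 calls steroid-refractory GVHD the primary risk of the rapid taper, and this is the plan's only numerical stopping boundary, in a pediatric de-escalation trial. The 15% reference rate is a day-100 rate, so any late case missing from the count tilts the comparison towards continuing.

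There are two weak points. First, a non-fatal case on days 57 to 100 is an SAE by 10.2.2. It is also expected by 10.2.3, because the protocol describes it, and so it falls outside the table's row for that period. A site reading 10.1, 10.2.1, 10.2.2 and the table together cannot tell which rule applies. Second, patients enrolled within the last 100 days have incomplete follow-up. If they are counted in k, they can raise the boundary before their own outcomes are complete.

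**Working it through.** **1. Reproducing the plan's figures.** Inputs from 10.6: b_k = 4, 5, 6, 7, 8, 9, 10, 11, 12, 13 for k up to 11, 15, 19, 23, 27, 32, 36, 41, 46, 50, stopping when failures exceed b_k. With each outcome known at enrollment,

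P_k(x) = (1 − p)·P_{k−1}(x) + p·P_{k−1}(x − 1),

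where the mass with x > b_k is removed at each k and summed as stopping.

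| True rate | Stated | Exact, k to 50 | Exact, k to 49 |
|---|---|---|---|
| 15% | 0.05 | 0.051 | 0.050 |
| 30% | 0.76 (table 0.75) | 0.762 | 0.749 |
| 35% | 0.92 | 0.922 | 0.915 |

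The stated figures are correct for instant, complete outcomes. The last column is the like-for-like benchmark for halting before patient 50.

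**2. Patients with incomplete follow-up.** Section 14.2 gives 30 patients per year, and realistically completion within three years.
- 30 per year: 365.25 / 30 = 12.2 days between patients; 100 / 12.2 = 8.2 patients inside a 100-day window.
- 50 in three years: 1,095.75 / 50 = 21.9 days; 100 / 21.9 = 4.6 patients.

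**3. The two wordings can disagree.** Suppose the fifth case among the first 11 patients is recognised after patient 12 enrolls. On the first-k wording, 5 > 4, so accrual halts. On the enrolled wording, k = 12 and b = 5; 5 does not exceed 5, so accrual continues.

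**4. Effect of lag alone, no events lost.** Accrual is simulated as a Poisson process with the printed boundary. Event timing is an assumption, because the documents give none; the range runs from all events at day 28 to uniform over days 0 to 100. The table shows the probability of halting before patient 50; small ranges within a cell are differences between simulation runs.

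| Accrual, timing | Enrolled, 30% | Enrolled, 35% | First k, 30% | First k, 35% |
|---|---|---|---|---|
| No lag | 0.749 | 0.915 | 0.749 | 0.915 |
| 30/yr, all day 28 | 0.67–0.68 | 0.87–0.88 | 0.73–0.74 | 0.90 |
| 30/yr, uniform | 0.61 | 0.82–0.83 | 0.71 | 0.88–0.89 |
| 50 in 3 yr, all day 28 | 0.71 | 0.89 | 0.74 | 0.90–0.91 |
| 50 in 3 yr, uniform | 0.67 | 0.87 | 0.73–0.74 | 0.90 |

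At a 35% rate and 30 per year, mean enrollment when accrual stops (50 if the rule is never met) is about 26 to 30 on the enrolled reading and 24 to 26 on the first-k reading, against 22 with no lag. On the first-k reading the chance of ever crossing stays at 0.76 and 0.92; some crossings simply come after accrual has closed. At a 15% rate, at 30 per year, the enrolled reading halts in about 0.02 to 0.03 of trials and the first-k reading in about 0.05.

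**The case against.** The strongest reply is that the SAE table is not the only route to the count. Section 10.2.2 names this event an SAE for the purposes of the study. Section 10.1 requires related SAEs after day 56 with no condition on expectedness. Section 13.2 sends every section 9.1 endpoint, including 9.1.3, to the coordinating center by eCRF. Sections 7.7 and 8.2 require evaluation at flare, and a late refractory case in a day-28 responder would usually be a flare. Section 10.6 does not tie the count to SAE forms. The first-k wording is already printed, and the DSMC, the investigators or the IRB may stop the trial on other grounds.

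Much of this stands. A reader might infer that every case after day 56 is lost and that the rule would then rarely stop a harmful trial. The documents do not support that: it would need every other route to fail and a large share of events after day 56. What they report, under standard dosing, points to earlier timing: a 79% day-28 response rate (section 3.4) and flares in only 5% of ultra-low-risk patients (section 3.5).

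A reader might also infer that recent enrollees cannot yet have had an event. They can: section 9.1.3 includes worsening that requires a new line of therapy at any time, and lack of response by day 28. What they lack is a full 100-day window.

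The reply does not remove the conflict between the four reporting texts, the absence of a scheduled check after day 90, or the double wording of the denominator.

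**Conclusion.** The point holds in a limited form. For an expected, non-fatal case on days 57 to 100, the reporting texts contradict one another and the backup routes are incomplete. Under-counting is therefore possible, but its size cannot be stated from the documents.

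The denominator is ambiguous in a way that changes decisions. On the enrolled reading at a 35% true rate, lag alone takes the chance of halting before patient 50 from 0.915 to about 0.82 to 0.88 at 30 per year, or about 0.87 to 0.89 at 50 in three years. On the first-k reading it is about 0.89 to 0.90, a small cost. These figures rest on Poisson accrual, complete reporting and the assumed event timing. The printed boundary is computed correctly; its stated properties describe a trial without lag. The 0.75 against 0.76 at a 30% rate is trivial.

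**What to change.** 1. Reconcile 10.1, 10.2.1, 10.2.2 and the SAE table so that steroid-refractory GVHD through day 100 is reported to the coordinating center within 3 days, regardless of expectedness or attribution. Send the running count to the DSMC.
2. Add a remote status check at day 100, and use one window in 4.2.6 (and the matching synopsis objective), 10.6 and 14.1. If day 90 is chosen, the 15% reference rate must be recomputed for it.
3. In 10.6, state that the rule is met as soon as failures among the first j consecutively enrolled patients exceed b_j for any j, and delete the wording based on k enrolled.
4. Restate the stopping probabilities under the planned accrual and lag, with the event timing assumed, and print one figure at 30%.

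The cost is a few more SAE forms, one remote contact per patient, and slightly less favourable stated probabilities. The boundary values and sample size need not change.

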## 10.5 Reporting of Unanticipated Problems

Upon becoming aware of any incident, experience, or outcome (not related to an adverse event) that may represent an unanticipated problem involving risks to subjects or others, the investigator should assess whether the incident, experience, or outcome represents an unanticipated problem. The incident, experience or outcomes are considered unanticipated if it meets all of the following criteria:

1. Unexpected (not previously documented in terms of nature, severity, or frequency);
2. Causally related or possibly related to participation in the study; and
3. Suggests that the research places subjects or others at a greater risk of harm than was previously known or recognized.

If the investigator determines that the incident, experience, or outcome represents an unanticipated problem, the investigator must report it to the MAGIC Data Coordinating Center within 3 days of first awareness of the events, and to the local IRB as per local IRB policy.

## 10.6 Stopping Rules

The primary risk from a rapid steroid taper is the possibility of steroid-refractory GVHD. We will monitor the study subjects for the development of steroid-refractory GVHD. We will allow continuous accrual on to the study unless a stopping rule is met or the target accrual is reached. The study may also be stopped based on the recommendation of the investigators, the TCI DSMC, or the single IRB.

### Steroid-refractory GVHD:

We expect a rapid steroid taper to be safe for ultra-low risk patients given the high response rates and very low NRM observed in our preliminary data from patients treated with standard steroid doses. The primary risk to patients is the possibility that a rapid taper of steroids will result in GVHD that is non-responsive even to higher doses of steroids. In order to protect study subjects we have designed a stopping rule that will terminate the trial early if a rapid taper leads to an unacceptable incidence of steroid-refractory GVHD. Our preliminary data show that the incidence of steroid-refractory GVHD by day 100 of treatment using the definition in section 9.1.3 in pediatric patients with low risk (Minnesota standard risk/Ann Arbor 1) GVHD is 15%.

We will monitor the number of cases of steroid-refractory GVHD by day 100 in the entire study population and accrual will be halted if there is sufficient evidence that the rate of steroid refractory GVHD exceeds the acceptable target rate of 15% by more than 20% (35% unacceptable rate). If the cumulative number of patients that experience treatment failure is greater than the associated boundary value  $b_k$  listed in the table below, among the  $k$  patients enrolled in the trial, then accrual will be halted for safety considerations. Specifically, if more than 4 of the first 11 patients or more than 5 of the first 15, etc. develop steroid refractory GVHD, the trial will be halted for safety considerations.

Maximum # of Patients, $k$	Up to 11	12-15	16-19	20-23	24-27	28-32	33-36	37-41	42-46	47-50
Boundary, $b_k$	4	5	6	7	8	9	10	11	12	13

The operating characteristics of this stopping rule are as follows:

	True Steroid Refractory Rate		
	15%	30%	35%
Probability of Early Stopping	0.05	0.75	0.92

Using these boundaries, if the true steroid refractory rate is 15%, 30%, or 35%, the probability of stopping the trial early is 0.05, 0.76, and 0.92 respectively.

All the stopping rules were computed using the `toxbdry` function in R and calculations of this function are based on methods described in Chapter 12 of Jennison and Turnbull and in the illustrative paper by Ivanova, Qaquish and Schell. The boundary crossing probabilities under

the acceptable and unacceptable toxicity rates are 0.05 and 0.90 respectively and the boundaries are calculated starting from 10th patient.

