### 3.4 GVHD Biomarker Algorithm Identifies Patients with Low Risk GVHD

MAGIC has validated a biomarker-based risk stratification system that is more accurate than clinical symptoms at classifying GVHD severity. The MAGIC algorithm probability (MAP) define the Ann Arbor (AA) risk scores (1, 2 or 3) that identify patients at high risk for treatment failure as well as patients who respond well to steroids and would benefit from reductions in treatment. The MAP reflects the extent of GI crypt damage as measured by serum concentrations of ST2 and REG3a. The presence of GI crypt damage portends a worse outcome, even when GI symptoms are minimal or absent, while the absence of GI crypt damage predicts response to steroid treatment, even when GI symptoms are present. The MAP has also been validated as a response biomarker and more accurately predicts survival than clinical response.

Recently we validated the MAGIC algorithm at start of steroid treatment for GVHD in 194 children (median age 12y, range 0.3-21y). Ann Arbor 1 GVHD (65% of patients) represents the best risk group with 2% NRM and each increase in Ann Arbor score represented a highly significantly increase in risk for NRM [Figure 2]. An analysis restricted to children <12y yielded similarly significant results. The area under the curve (AUC) for NRM was significantly better for Ann Arbor scores than clinical severity (0.84 vs 0.63, p=0.007). Ann Arbor scores were predictive of outcomes regardless of onset GVHD severity and within subgroups such as graft type (marrow, peripheral blood, or cord blood), use of anti-thymocyte globulin during conditioning, or diagnosis.

[figure not shown]

Figure 2. NRM in 194 pediatric patients from start of steroid treatment by Ann Arbor score.

Further analyses demonstrated that the combination of favorable clinical features (Minnesota standard risk) and biomarkers Ann Arbor 1 score defines a **low risk** population with a good overall response rate (ORR) to steroids (79%), but the risk posed by a 20% treatment failure rate is a barrier to the rapid tapers likely needed to reduce steroid toxicities.

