#### **4.6 Safety Endpoints**

1. Proportion of patients who develop steroid refractory GVHD defined as GVHD that worsens by at least one stage in at least one target organ **and** requires systemic treatment with an agent other than steroids

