#### **9.1.3 Steroid refractory GVHD**

Steroid refractory GVHD is defined as either an increase by at least one GVHD stage that requires initiation of an additional line of therapy beyond steroids or a lack of response (i.e., NR) by day 28. Escalation of steroid doses during treatment for GVHD are not considered in the definition of steroid refractory GVHD. The resumption or addition of tacrolimus, sirolimus, or cyclosporine will not be considered a new line of treatment.

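### The steroid-refractory stopping rule rests on a 15% benchmark that conflicts with the plan's own 79% response rate under the definition it cites; if events are counted that way, the chance of a false halt is about 0.21 to 0.27, not 0.05.

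*Combined protocol and SAP*

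**What the plan says.** Section 10.6 contains the trial's only numerical stopping boundary.

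- **Benchmark.** The incidence by day 100 "using the definition in section 9.1.3 in pediatric patients with low risk (Minnesota standard risk/Ann Arbor 1) GVHD is 15" percent.
- **Scope.** "We will monitor the number of cases of steroid-refractory GVHD by day 100 in the entire study population".
- **Trigger.** Accrual halts on sufficient evidence that the rate "exceeds the acceptable target rate of 15% by more than 20% (35% unacceptable rate"). In counts, the trial is halted "if more than 4 of the first 11 patients or more than 5 of the first 15, etc. develop steroid refractory GVHD". The boundary rises to 13 at patients 47 to 50.
- **Operating characteristics.** At true rates of 15%, 30% and 35%, "the probability of stopping the trial early is 0.05, 0.76, and 0.92 respectively". The table just above that sentence prints 0.75 for the 30% rate.

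The event is defined in two ways:

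- Section 9.1.3 has two limbs: a stage increase that leads to another line of therapy, "or a lack of response (i.e., NR) by day 28". Section 9.1.1 makes NR everything other than CR, VGPR or PR, and scores patients given other systemic GVHD therapy as NR on day 28.
- Section 4.6 has "steroid refractory GVHD defined as GVHD that worsens by at least one stage in at least one target organ" and also requires a systemic agent other than steroids. It has no non-response limb.

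For Minnesota standard risk/Ann Arbor 1 disease, section 3.4 reports an "overall response rate (ORR) to steroids (79%), but the risk posed by a 20% treatment failure rate". Section 3.5 splits 85 children in that risk group into 65% with a 96% response rate and the remaining 35% with 47%.

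**The concern.** Under section 9.1.3 a patient who is NR at day 28 is already a case, so the refractory rate by day 100 cannot be lower than the day-28 non-response rate in the same patients. A 79% response rate puts that floor near 21%, yet the benchmark tied to this definition is 15%.

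What is at stake is whether the monitoring committee can apply the rule as described. Counted under 9.1.3, as section 10.6 directs, the rule may halt a regimen that performs no worse than current practice far more often than the stated 5%. Counted under 4.6, it monitors a different event from the one section 10.6 names. Section 10.2.2 also makes steroid-refractory GVHD a serious adverse event, so the choice of definition affects SAE reporting as well.

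**Working it through.** **Step 1. Reproduce the plan's figures.** Inputs: the section 10.6 boundary, b = 4 (up to patient 11), 5 (12–15), 6 (16–19), 7 (20–23), 8 (24–27), 9 (28–32), 10 (33–36), 11 (37–41), 12 (42–46), 13 (47–50).

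Let P_k(s) be the probability that the trial is still open after k patients with s cases. Then P_k(s) = P_{k−1}(s)(1 − p) + P_{k−1}(s − 1)p. At each k, the mass with s > b_k moves to "stopped". The stopping probability is the mass moved over k = 1 to 50.

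| True rate p | Recomputed | Section 10.6 |
|---|---|---|
| 15% | 0.051 | 0.05 |
| 30% | 0.762 | 0.76 in text, 0.75 in table |
| 35% | 0.922 | 0.92 |

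The boundary is sound for its stated input. Starting the looks at patient 1, 5, 10 or 11 makes no difference. Omitting the look at patient 50 gives 0.749 at 30%, which might explain the 0.75.

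**Step 2. Non-response implied by the plan.**

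- Section 3.4, printed failure rate: 20%.
- Section 3.4, from the response rate: 1 − 0.79 = 21%.
- Section 3.5, weighted: 0.65 × 0.96 + 0.35 × 0.47 = 0.624 + 0.1645 = 0.7885, so non-response is 21.15%.
- As a count, assuming the figure rests on the 85 children: 85 × 0.2115 ≈ 18, and 18/85 = 21.2%. The plan does not print this count.
- Section 3.8 gives a 75% response rate in the Ann Arbor 1 subset made eligible in 2023, that is 25% non-response.

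Under 9.1.3, patients who respond at day 28 and become refractory by day 100 add to these figures.

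**Step 3. The printed boundary at those rates.**

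| True rate p | Probability of halting |
|---|---|
| 20% | 0.210 |
| 21% | 0.259 |
| 21.15% | 0.267 |
| 21.2% | 0.270 |
| 25% | 0.490 |

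Against 0.05, the range 0.21 to 0.27 is about four to five times as high.

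**Step 4. Could sampling error account for the gap?** If 18/85 is the source (assumed), the exact 95% confidence interval for non-response is about 13% to 31%. It contains 15%.

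**The case against.** A reader might infer that the 79% response rate rules out 15%. The documents do not support that. Section 10.6 attributes the 15% to preliminary data without a sample size or named cohort. Section 3.4 gives the 79% without a sample size, and that sentence does not state day 28. Nothing says that the two figures describe the same children, and the interval in step 4 includes 15%. This objection stands: the conflict is between point estimates under a cited definition and is not a proof that the benchmark is impossible.

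A reader might also take 27% as the trial's false-stop risk. It is conditional on counting under 9.1.3 and on a true rate near 21.2%, which is derived and not printed. At the plan's own printed failure rate of 20% the figure is 0.21. If the 15% was obtained under section 4.6 and cases are counted that way, the stated 0.05 is right. This stands too.

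It may be said that a lack of response by day 28 means never having responded, which would lower the floor. This is weak, because section 9.1.3 equates the phrase with NR, and section 9.1.1 scores NR on day 28.

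Finally, a reader might infer that patients are less protected than stated. They are not: an acceptable rate set too low makes the rule halt too readily, and the stopping probability at 35% remains 0.92. The cost is a possible needless halt.

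**Conclusion.** The concern holds in a conditional form. Sections 4.6 and 9.1.3 define steroid-refractory GVHD differently; that is certain from the text. Section 10.6 ties its 15% benchmark to 9.1.3, and the plan's own response figures for that risk group imply about 20% to 21% from day-28 non-response alone. The two do not fit together as written.

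The boundary arithmetic is correct, and the difficulty lies in the input and the definition. The stopping probability of 0.21 to 0.27 for a regimen no worse than current practice rests on two assumptions: events are counted under 9.1.3, and the true rate equals the historical non-response rate. The 0.49 at 25% would apply if later refractory cases, or a case mix like the newly eligible subset, raised the rate that far. That 15% arose under the 4.6 definition is possible, but the documents do not say so.

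**What to change.** 1. Reconcile sections 4.6, 9.1.3, 10.2.2 and 10.6 to one definition of the monitored event.
2. Re-tabulate the historical rate by day 100 under that definition in the MAGIC low-risk pediatric cohort, and report the number of patients and of cases.
3. Restate the operating characteristics:
   - If 15% was obtained under the 4.6 definition, cite and count that event in 10.6. The current table stands.
   - If 9.1.3 is kept, either recompute the boundary from the re-tabulated rate, or keep the present boundary and state its stopping probability at that rate. Print any new boundary patient by patient.
4. Correct the 0.75 versus 0.76 at the 30% rate.

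The cost is one tabulation of existing data, at most one boundary run, and a protocol wording change. The trade-off under 9.1.3 is that a boundary recalibrated to 0.05 at a higher acceptable rate will stop less often at 35%. As an indication, one built by the same method (constant tail probability, starting at patient 10) for 21.2% stops with probability about 0.62 at 35%, against 0.92 now. The monitoring committee should see that figure before choosing.
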